1.4 Do you need funding from Assiut Medical School Grants Office?

Yes

No

Mention other sponsoring agent(s) if any: .....

## Part 2: Research Details

### 2.1 Background (Research Question, Available Data from the literature, Current strategy for dealing with the problem, Rationale of the research that paves the way to the aim(s) of the work). (200-250 words max.)

Pilonidal disease derives its name from Latin- pilus meaning “hair,” and nidus meaning “nest” (1). The source of pilonidal disease is thought to be a deep intergluteal sulcus. It is widely accepted that the establishment of the pilonidal sinus results from the penetration of shed hair shafts through the skin, which ultimately leads to an acute or chronic infected site (2).

Pilonidal disease is largely considered a surgical disease, especially in acute instances with secondary infection and abscess. Infection or abscess requires incision and drainage. Definitive treatment is delayed the majority of the time if there is an acute infection or abscess until after the infection has been addressed. Surgical options for chronic disease are numerous and can include “pit picking,” curettage, aspiration, unroofing, or surgical excision. Defects can be closed primarily, with flaps or grafts, or allowed to heal by secondary intention (3-5).

The most serious problem of the various surgical approaches proposed is the recurrence rate, ranging from 0% to 40% (6, 7).

The surgical treatment of patients with recurrent disease does not differ from the surgical treatment of primary pilonidal disease. In case of a recurrence with an abscess, incision and drainage prevail, while in case of chronic recurrent disease, a flap based procedure may be indicated following sinus excision with scarring, like the rhomboid flap (8, 9).

To the best of our knowledge, the existing literature is poor with studies comparing flap-based techniques with deep suturing (or primary closure) techniques in the management of recurrent pilonidal disease.

### 2.2 Aim(s) of the Research (50 words max):

This prospective clinical trial aims to compare the perioperative outcomes of rhomboid flap versus deep suturing in the management of recurrent sacrococcygeal pilonidal disease.

### 2.3 Research Domain (Faculty Research Plan).

Evidence-based management of a common surgical problem.

### 2.4. Research Methods and techniques:

2.4.1- **Type of the study:** A randomized controlled Clinical Trial

2.4. 2- **Study Setting:** General Surgery Department, Assiut University Hospitals.

2.4. 3- **Study subjects:**

**a. Inclusion criteria:**

- b. Adult patients aged between 18 and 60 years;
- c. Patients with one or two small inactive sinuses will be included for easier excisional procedures;
- d. Previous intervention for pilonidal disease whether surgical or non-surgical;

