**b. Exclusion criteria:**

- 1- Patients with an acute abscess.
- 2- Patients with small inactive pilonidal sinus disease.
- 3- Age beyond the previous limits.
- 4- Patients with primary pilonidal disease.
- 5- Refusal to participate in the study.
- 6- Unfit for anaesthesia and surgery.
- 7- Patients with malignant neoplasms or inflammatory bowel disease.

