**c. Sample Size Calculation:**

The required sample size was calculated using the IBMa SPSSa Sample Powera version 3.0.1 (IBMa Corp., Armonk, NY, USA). A previous study conducted by Cihan et al. reported that the incidence of recurrence after Rhomboid Flap was 5.71% (9). Thus, it was estimated that a minimal sample size of **32 patients** is required to achieve a power of 80% to detect expected difference of 14 % in the incidence of recurrence, at a significance level of 0.05. An equal number will be recruited in the deep closure group.

2.4.4 –**Study tools (in detail, e.g., lab methods, instruments, steps, chemicals, ...):**

All patients will be subjected to complete history taking (focusing on the duration since the primary operation, symptoms and its duration), thorough physical examination, and routine preoperative blood tests (CBC, renal function, liver function, prothrombin time, random blood glucose). Additionally, conventional or magnetic resonance sinogram will be ordered when required.

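### The inclusion list admits patients with small inactive sinuses and the exclusion list rejects them, so the entry rule cannot be followed as written

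*Protocol*

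**What the plan says.** Section 2.4.3 of the Protocol lists three inclusion items, lettered b to d, and seven exclusion items.

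- Inclusion item b sets the age range, 18 to 60 years.
- Inclusion item c: "Patients with one or two small inactive sinuses will be included for easier excisional procedures".
- Inclusion item d: "Previous intervention for pilonidal disease whether surgical or non-surgical".
- Exclusion item 2: "Patients with small inactive pilonidal sinus disease".
- Exclusion item 4: "Patients with primary pilonidal disease".

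The other exclusions cover acute abscess, age, refusal, fitness for anaesthesia and surgery, and malignancy or inflammatory bowel disease.

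Section 2.2 gives the aim as a comparison of "rhomboid flap versus deep suturing in the management of recurrent sacrococcygeal pilonidal disease". It does not mention the size, number or activity of the sinuses.

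**The concern.** Inclusion item c and exclusion item 2 use the same two descriptors, small and inactive, for the same condition and give opposite instructions. A recruiter facing a previously treated patient with one such sinus must break one of the lines: enrolling breaches exclusion item 2, and refusing contradicts inclusion item c.

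What is at stake is whether small inactive disease is in the trial at all. That decides to whom the primary comparison, the postoperative recurrence rate, applies. If recruiters resolve the conflict differently, or one recruiter changes practice during the trial, the mix of patients will depend on unrecorded judgement. Any enrolment of a patient covered by item c could also later be called an eligibility deviation.

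**Working it through.** The point is one of logic. The plan states no figure to reproduce.

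**1. The two lines side by side**

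| | Inclusion item c | Exclusion item 2 |
|---|---|---|
| Size | small, no threshold | small, no threshold |
| Activity | inactive, undefined | inactive, undefined |
| Number of sinuses | one or two | not limited |
| Primary or recurrent | not stated | not stated |
| Instruction | include | exclude |

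The only difference in scope is the number of sinuses, and there item c is the narrower line. The patients it names are a subset of those whom exclusion item 2 removes, so no patient satisfies item c and escapes exclusion item 2.

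**2. Does anything else in the protocol separate them?**

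- Inclusion item d requires earlier treatment but says nothing about size or activity.
- Exclusion item 1 (acute abscess) concerns a different presentation.
- Exclusion item 4 already removes primary disease. With it in place, the only patients exclusion item 2 can newly remove are those with recurrent disease, which is the group the trial is meant to recruit.
- The aim in section 2.2 specifies recurrent disease but not its extent.

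No other section defines small or inactive.

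**3. What each way of handling the conflict would admit**

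Take three disease profiles, with all other criteria met:

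- A: small and inactive, one or two sinuses
- B: small and inactive, three or more sinuses
- C: not both small and inactive

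Rules: if item c is required, only A can pass. If item c is permissive or deleted, it restricts nobody. If exclusion item 2 applies, A and B are rejected.

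| Handling | Eligible profiles |
|---|---|
| Both lines applied, item c required | none (0 of 3) |
| Both lines applied, item c permissive | C (1 of 3) |
| Item c deleted | C (1 of 3) |
| Exclusion item 2 deleted, item c required | A (1 of 3) |
| Exclusion item 2 deleted, item c permissive | A, B, C (3 of 3) |

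The first two rows are readings of the present text. The other three show what would follow from deleting one line. Profile A, the one item c names, is ineligible wherever exclusion item 2 is applied and eligible wherever it is not. Two of the possible resolutions, C only and A only, share no patients. The profiles are constructed to show the logic, and the counts do not estimate how many patients are affected.

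**The case against.** The best defence is that the conflict is loose drafting with a recoverable meaning. Exclusion lists often repeat inclusion criteria, and this one does: exclusion item 3 restates the age limits, and exclusion item 4 largely restates the need for earlier treatment in inclusion item d. Exclusion item 2 might likewise be an imprecise way of keeping out quiescent, untreated disease, in which case it would not touch the recurrent patients in item c. This has some force. Because the list contains other repetition, the overlap with exclusion item 4 does not by itself prove that item 2 was aimed at recurrent disease. But the defence needs a qualifier that the text lacks, and item c uses the same word, inactive, for patients who are to have an excision.

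A second argument is that item c, with its reason attached, reads as permission rather than a requirement, so the trial is not empty. That is a fair reading, and the result that nobody is eligible should be taken as conditional. It does not remove the contradiction, because the permitted patients are still excluded.

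Third, most of the population is defined: age, earlier treatment, no abscess, no primary disease, fitness for surgery. Only the extent and activity of disease are unsettled. In a randomised trial an unclear entry rule applied before allocation need not bias the difference between arms. Both statements stand, and they limit the harm to consistency of enrolment and to whom the result applies.

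Finally, a link to the sample size is unproven. The calculation relies on a previous study in which "the incidence of recurrence after Rhomboid Flap was 5.71" per cent, and the protocol does not describe the disease extent in that study. Nothing in the document shows that the rate would change, or in which direction.

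**Conclusion.** The contradiction is real and must be corrected. Inclusion item c and exclusion item 2 cannot both be followed for the patients item c names. As the text stands, the trial admits nobody if item c is required, and only patients whose disease is not both small and inactive if item c is permissive.

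This rests on reading the two lines as written, with no unstated qualifier on either. It does not rest on the profile counts or on any claim that the sample size is wrong. The consequence is an entry rule that leaves disease extent and activity unresolved, and with it the population to which the recurrence comparison applies. It is not in itself a source of bias between arms, provided the decision to enrol is made without knowledge of the allocation.

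**What to change.** Before any further enrolment, the sponsor should reconcile the two lines in section 2.4.3 in one of these ways:

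1. Delete inclusion item c.
2. Delete exclusion item 2.
3. Replace both with one criterion that states an explicit, non-overlapping boundary in number, size and activity of sinuses.

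If item c is kept, the text should say whether it is a required condition or only allows such patients to enter, because with exclusion item 2 deleted that decides between profile A alone and all three profiles. If exclusion item 2 was meant for a different group, that group should be named. Which population is intended is the sponsor's decision.

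Once it is settled, check that the 5.71% recurrence assumed in the sample size section suits that population. Whether the sample size changes depends on that check and cannot be told from the protocol.

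The cost is a short amendment to the eligibility text and one recheck of the recurrence assumption. If patients have already been enrolled, their eligibility should be reviewed against the corrected wording.

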**b. Exclusion criteria:**

- 1- Patients with an acute abscess.
- 2- Patients with small inactive pilonidal sinus disease.
- 3- Age beyond the previous limits.
- 4- Patients with primary pilonidal disease.
- 5- Refusal to participate in the study.
- 6- Unfit for anaesthesia and surgery.
- 7- Patients with malignant neoplasms or inflammatory bowel disease.

**c. Sample Size Calculation:**

The required sample size was calculated using the IBMa SPSSa Sample Powera version 3.0.1 (IBMa Corp., Armonk, NY, USA). A previous study conducted by Cihan et al. reported that the incidence of recurrence after Rhomboid Flap was 5.71% (9). Thus, it was estimated that a minimal sample size of **32 patients** is required to achieve a power of 80% to detect expected difference of 14 % in the incidence of recurrence, at a significance level of 0.05. An equal number will be recruited in the deep closure group.

2.4.4 –**Study tools (in detail, e.g., lab methods, instruments, steps, chemicals, ...):**

All patients will be subjected to complete history taking (focusing on the duration since the primary operation, symptoms and its duration), thorough physical examination, and routine preoperative blood tests (CBC, renal function, liver function, prothrombin time, random blood glucose). Additionally, conventional or magnetic resonance sinogram will be ordered when required.

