**The rhomboid flap Approach (32 patients)**

The patient will be operated on under spinal anesthesia. The patients will be placed in prone jack-knife position on the operating table with the legs slightly abducted and the buttocks strapped apart by adhesive tapes. The anus will be excluded from the operative field by surgical drapes. The pathologic area to be excised will be marked. This area will be

enclosed by a rhombus shape with the long axis in the midline (ABCD). Lines  $AB = BC = CD = DA$  will be equal to each other, with the axis AC being along the natal cleft. Line BD will be extended transversely and then the line EF will be drawn equal in length. The rhombus containing the pilonidal sinus will be then excised down to the periosteum in the midline and gluteal fascia laterally. Meticulous hemostasis will be done by means of electrocautery.

The flap will be dissected deep to the gluteal fascia (subfascial level) so as to raise thick a fasciocutaneous flap. This will assure good vascularity of the flap without dead space. The rhomboid flap (CDEF) will be mobilized from the gluteal fascia and sutured without tension in three layers (gluteal fascia with 2/0 Vicryl, subcutaneous fat with 3/0 Vicryl, and the skin with 4/0 Prolene). As all sides will be equal in length, the flap fits in place without tension. A suction drain will be left behind and the wound will be dressed as usual. Pressure wound dressing will be applied and removed on the third postoperative day.

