#### **The deep suturing approach (32 patients)**

A vertical elliptical incision encompassing all pilonidal pits will be made and excision of the sinus will be carried out down to the level of the sacrococcygeal fascia. Tension will be released by a limited sharp dissection above the fascia. After haemostasis is ensured using electrocautery, a suction drain will be inserted through a separate incision, then the deep fascia will be approximated and the wound will be closed in layers using polyglactin 0 sutures. Finally, the skin will be closed with 2/0 polypropylene interrupted mattress sutures.

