##### Statistical tests

Quantitative data will be presented as means  $\pm$  SD. Categorical and binary variables will be tested using the  $\chi^2$  test and Fisher's exact test. Statistical significance will be assumed when  $p < 0.05$ .

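### 32 patients per group gives about 23–42% power for the 14-point difference in recurrence, not the stated 80%; the 32 matches a one-sample formula

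*Protocol*

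**What the plan says.** The Protocol, section 2.4.3 c (Sample Size Calculation), gives one literature rate, from a study that "reported that the incidence of recurrence after Rhomboid Flap was 5.71% (9"). It concludes that a group of at least 32 "is required to achieve a power of 80% to detect expected difference of 14 % in the incidence of recurrence". Alpha is set to 0.05. The next sentence brings in the comparator: "An equal number will be recruited in the deep closure group". The headings in section 2.4.4 confirm the group sizes: "The rhomboid flap Approach (32 patients") and "The deep suturing approach (32 patients").

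The design is a randomised controlled trial (2.4.1) and the primary outcome is recurrence (2.4.5 a). Section 2.5 names the chi-square test and Fisher's exact test for binary variables, with significance at p < 0.05.

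The Protocol does not state the recurrence rate expected after deep suturing, whether the test is one- or two-sided, which formula was used, or any allowance for loss to follow-up.

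**The concern.** Two things in the paragraph suggest an error. First, 32 per group is very small for telling apart two recurrence rates that differ by 14 points. Second, the number is derived from one rate, and the second group is added only afterwards, as if it had played no part in the calculation. A one-sample calculation treats the reference rate as known without error. This trial estimates both rates, each in 32 patients, so the difference carries the sampling error of both groups.

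The primary question is at stake. If real power is far below 80%, the trial will probably miss the difference it was designed to find. A reader who trusts the stated 80% could then take a non-significant result as evidence that recurrence is similar after the two operations. The ethics committee, too, is being told that the trial can answer a question that it probably cannot.

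**Working it through.** **Inputs from section 2.4.3 c**
- Rhomboid flap rate: p1 = 0.0571.
- Difference: 0.14, read as percentage points. Since 0.0571 − 0.14 is negative, the deep suturing rate is p2 = 0.0571 + 0.14 = 0.1971.
- Power 80% (z = 0.8416) and alpha 0.05. Two-sided testing (z = 1.960) is taken as the base case, because sidedness is not stated.
- Group sizes: 32 and 32.

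**Step 1. Reproduce the stated 32**

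One-sample test of p2 against a fixed p1:

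n = [1.960·√(p1(1−p1)) + 0.8416·√(p2(1−p2))]² / 0.14²

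= [1.960·√(0.0571·0.9429) + 0.8416·√(0.1971·0.8029)]² / 0.0196

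= (0.4548 + 0.3348)² / 0.0196 = **31.8, rounded up to 32**

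This is the stated figure.

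**Step 2. Sample size for two groups**

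The mean rate is p̄ = (0.0571 + 0.1971)/2 = 0.1271.

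n per group = [1.960·√(2p̄(1−p̄)) + 0.8416·√(p1(1−p1) + p2(1−p2))]² / 0.14²

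= (0.9232 + 0.3876)² / 0.0196 = **87.7, rounded up to 88**

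| Method | Two-sided, per group | One-sided, per group |
|---|---|---|
| Pooled normal approximation | 88 | 69 |
| Unpooled variance | 85 | 67 |
| Arcsine | 83 | 65 |
| With continuity correction | 102 | 83 |
| Fisher, exact enumeration | about 96 | not computed |

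No two-group version comes near 32 per group.

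**Step 3. Power with 32 per group, 5.71% vs 19.71%**

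Normal approximation, two-sided:

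z = (0.14·√32 − 0.9232) / √(p1(1−p1) + p2(1−p2)) = (0.7920 − 0.9232)/0.4605 = −0.285, so power = Φ(−0.285) = **38.8%**

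Exact enumeration over all pairs of binomial counts:

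| Test | Two-sided | One-sided |
|---|---|---|
| Fisher's exact | 23.3% | 34.8% |
| Uncorrected chi-square | 41.8% | 55.8% |

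**Step 4. What the trial would probably show**

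Expected recurrences are 32 × 0.0571 = 1.8 and 32 × 0.1971 = 6.3, so about 2 against 6. For 2/32 vs 6/32, Fisher p = 0.26 and chi-square p = 0.13. The difference is 12.5 points, with a 95% CI of 12.5 ± 1.96 × 8.12, or about −3 to +28 points. With 8 events in total, the expected count under the null hypothesis is 4 per group. That is below the usual threshold of 5 for chi-square, so Fisher's test, the weaker of the two here, is likely to be the one used.

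**Step 5. What 32 per group can detect**

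Two-sided power reaches 80% at a difference of about 26 points with chi-square (25.6), 27 points by the normal approximation and 30 points with Fisher (29.5). The deep suturing rate would have to be roughly 31% to 35%.

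**Step 6. Other readings**
- 14% as the deep suturing rate itself: two-sided power of 7% to 21%.
- 32 as the total (16 per group): 9% (Fisher) to 19% (chi-square).

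**The case against.** The strongest objection is that the Protocol names a software package but no formula, so the one-sample origin cannot be proved. Other routes land nearby. A one-sided one-sample arcsine calculation gives 32.3. A one-sided two-group arcsine calculation gives 64.6 per group, which is close to the trial's total of 64 if misread as a total. This stands, and the one-sample origin should be called likely, not established. It does not rescue the stated power, because all of these routes lead to the same underpowered two-group comparison.

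Nor does the Protocol state sidedness or the 19.71% rate. The 23–42% range is two-sided, and the reading most favourable to the plan is one-sided. That reading gives 35% to 56%, still well short of 80%.

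It can also be said that how the result is reported and interpreted may belong in an SAP that is not shown, and that the Protocol nowhere claims equivalence. That is fair, and such advice is kept apart from the correction below. The power claim is different: the Protocol makes it, and no later analysis plan can make 32 per group deliver it.

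**Conclusion.** The concern holds. For 5.71% against 19.71% at two-sided 0.05, the planned 32 per group gives between 23% (Fisher) and 42% (chi-square) power, which is about half the stated 80% or less. Keeping 80% would take 88 per group by the standard formula, or 2.75 times the planned number (88/32).

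The figures assume that 14% means percentage points, that testing is two-sided and that nobody is lost to follow-up; any loss lowers power further. The conclusion survives changes to the first two: no one-sided, arcsine, continuity-corrected or exact two-group version tried gives 80% at this size. The one-sample explanation for the 32 fits the number and the order of the text, but it remains an inference and the conclusion does not rest on it.

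**What to change.** Rewrite the sample size paragraph in section 2.4.3 c so that it:
- describes a comparison of two independent proportions, with the deep suturing rate (19.71%) and the sidedness written out;
- drops the claim that 32 patients give 80% power for 14 points;
- states that 32 per group has about 42% power with chi-square (39% by the normal approximation) and 23% with Fisher's exact test for 5.71% vs 19.71%;
- states that 80% power is reached only for a difference of about 26 points (chi-square) to 30 points (Fisher).

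The cost is one paragraph of wording and a less favourable power statement. It adds no patients and no procedures.

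For information, keeping 80% power for 14 points would take about 88 per group (176 in total) with chi-square or about 96 per group (192) with Fisher, before any loss to follow-up.

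As an option, here or in the SAP, report the primary result as a risk difference with a 95% CI and say in advance that a non-significant result will not be read as equal recurrence.

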**The rhomboid flap Approach (32 patients)**

The patient will be operated on under spinal anesthesia. The patients will be placed in prone jack-knife position on the operating table with the legs slightly abducted and the buttocks strapped apart by adhesive tapes. The anus will be excluded from the operative field by surgical drapes. The pathologic area to be excised will be marked. This area will be

enclosed by a rhombus shape with the long axis in the midline (ABCD). Lines  $AB = BC = CD = DA$  will be equal to each other, with the axis AC being along the natal cleft. Line BD will be extended transversely and then the line EF will be drawn equal in length. The rhombus containing the pilonidal sinus will be then excised down to the periosteum in the midline and gluteal fascia laterally. Meticulous hemostasis will be done by means of electrocautery.

The flap will be dissected deep to the gluteal fascia (subfascial level) so as to raise thick a fasciocutaneous flap. This will assure good vascularity of the flap without dead space. The rhomboid flap (CDEF) will be mobilized from the gluteal fascia and sutured without tension in three layers (gluteal fascia with 2/0 Vicryl, subcutaneous fat with 3/0 Vicryl, and the skin with 4/0 Prolene). As all sides will be equal in length, the flap fits in place without tension. A suction drain will be left behind and the wound will be dressed as usual. Pressure wound dressing will be applied and removed on the third postoperative day.

